7.5 Long-term Follow-Up Assessments

At one, three, and six months post-transplant the CRA(s) or investigators will meet with subjects to complete self-report assessments for depression (PROMIS-D), post-traumatic stress symptoms (PTSS-14), and HRQOL (FACT-BMT), as well as clinician-rated assessments of cognition (MOCA) and functional status (ECOG-PS). At the time of each follow-up, delirium assessments (DRS) will also be performed in participants who became delirious during the inpatient phase. Subjects will receive reminders regarding these long-term assessments via subjects' preferred method of contact. Long-term assessments will occur at one month (+/- two weeks), three months (+/- four weeks), and six months (+/- two months). The specified window at each of these follow-up time points will allow for assessments to coincide with BMT clinic visits. If a face to face assessment is not feasible, attempts will be made to perform assessments over the phone, through video conferencing, online, by email, or by mail. When assessments cannot be completed, this will be noted in the eCRF.

7.6 Concurrent CNS Active Medications

All concurrent CNS active medications, including antidepressants, anxiolytics, antipsychotics, antiepileptics, and antihistamines will be documented at Baseline/Screening and throughout the study as summarized in the Time and Events Table in Section 7.1.

7.7 Demographics

Demographic information (date of birth, gender, race) will be recorded by the CRA from review of medical records at baseline.

7.8 Delirium Risk Factors

Relevant risk factors for delirium, including previous history of delirium, alcohol and substance use, and neurological conditions (stroke, traumatic brain injury, seizures, abnormal findings on imaging) will be abstracted from medical records at baseline.

7.9 Handling of Biospecimens Collected for Correlative Research

Biospecimens for this study will be collected by a registered nurse and stored in the McLendon laboratories. Blood samples will then be sent Mayo Medical

Laboratories for assay of thiamine levels. Each sample will be assigned a unique code number and no identifiable personal health information (PHI) will be on the specimen label. Researchers with IRB-approval for access to PHI for each subject in this study will be able to link specimens to relevant medical information.

Storage Time:

- The biospecimen will be used first and foremost for research purposes outlined within the confines of this protocol. Samples will be discarded/destroyed after relevant data are collected for this study, unless consent was obtained from the patient to use his/her blood for other research purposes (e.g., consent form was signed by the patient). In this circumstance, there is no time limit on how long biospecimens may be stored.

Compliance Statement

Biospecimen collection for this study will be conducted in full accordance with all applicable University of North Carolina (UNC) Research Policies and Procedures and all applicable Federal and state laws and regulations including 45 CFR 46, and the Health Insurance Portability and Accountability Act (HIPAA) Privacy Rule. Any episode of noncompliance will be documented.

The investigators will perform the study in accordance with this protocol, will obtain consent and assent (unless a waiver is granted), and will report unexpected problems in accordance with The UNC IRB Policies and Procedures and all federal requirements. Collection, recording, and reporting of data will be accurate and will ensure the privacy, health, and welfare of research subjects during and after the study.

7.10 Assessment of Safety

Any patient who receives at least one dose of study therapy on this protocol will be evaluable for toxicity. Each patient will be assessed periodically for the development of any toxicity according to the Time and Events table. Toxicity will be assessed according to the NCI CTCAEv4.0.3.

7.11 Assessment of Efficacy

In order to be considered evaluable for efficacy, patients must:

- receive all 7 days of the treatment; a patient must receive at least 17/21 (80%) thiamine doses
- have delirium assessed at least weekly until one of the following is met:
 1. The participant is found to be delirious (DRS>12)
 2. The participant is at least 30 days post-transplant
 3. The participant is discharged

If a patient is deemed not evaluable, they will be replaced by a new patient. However, if a patient develops delirium during the intervention, they will still

receive the full 7 day course, not be replaced, and included in the efficacy analysis.

8.0 ADVERSE EVENTS

8.1 Definitions

8.1.1 Adverse Event (AE)

An adverse event (AE) is any untoward medical occurrence (e.g., an abnormal laboratory finding, symptom, or disease temporally associated with the use of a drug) in a patient or clinical investigation subject administered a pharmaceutical product and which does not necessarily have a causal relationship with this treatment. An AE can therefore be any unfavorable and unintended sign (including an abnormal laboratory finding), symptom, or disease temporally associated with the use of a medicinal product, whether or not related to the medicinal product.

Hospitalization for elective surgery or routine clinical procedures that are not the result of an AE (e.g., surgical insertion of central line) need not be considered AEs and should not be recorded as an AE. Development or worsening of delirium should not be recorded as an AE, unless it is attributable by the investigator to the study therapy.

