3.0 Criteria for Evaluation / Study Endpoints

3.1 Primary Endpoint

Delirium incidence will be defined as: DRS > 12. Delirium rating scales will be performed at baseline (prior to transplant) and then three times weekly from day after transplant to 30 days after transplant or discharge, whichever comes first.

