5.2 Treatment Dosage and Administration

Subjects in the intervention group will receive thiamine 200 mg IV tid for seven days beginning on the day after of transplant. Subjects in the control group will receive 100 mL (equivalent volume to intervention) normal saline IV tid for seven days beginning on the day after transplant. All investigators will be blinded to which patients are assigned to which arm of the study. Only the Investigational Drug Service (IDS) will be aware of which patients will be assigned to which arms. At any time, the PI, primary medical providers, or other emergency personnel may request unblinding of a subject’s randomized treatment from IDS. If there is an adverse reaction, subjects will be treated symptomatically and consideration will be given to stopping the medication, as outlined in Section 5.3.

REGIMEN DESCRIPTION				
Group	Agent	Dose	Route	Schedule
Intervention	Thiamine	200 mg Thiamine HCL solution in 100 mL infusion bag of 0.9% Sodium Chloride	IV over 30 minutes (50 ml/hr)	Post-transplant Days 1 – 7 three times daily

Control	Normal Saline	100 mL of 0.9%	IV over 30 minutes (50 ml/hr)	Post-transplant Days 1 – 7 three times daily
---------	---------------	----------------	-------------------------------	--

Prescribing Information

Full prescribing information for thiamine can be found at the following web address: http://editor.fresenius-kabi.us/Pis/Thiamine_Inj_45819E_May_08.pdf

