7.4 Post-Transplant Days 1 – 30 Assessments

Within two days of transplant, the subject will have a CBC, CMP, Mg level, Phos level, and Thiamine level drawn. The CRA(s) or investigators will perform the delirium assessment (DRS), and a brief history will be obtained to assess for any toxicity from therapy.

Over the course of 30 days following transplant (or discharge, whichever comes first), the subject will continue to have weekly thiamine levels drawn (at days 8, 15, 22, and 29 +/- one day). The CRA(s) or investigators will continue to assess for delirium, using the DRS, three times weekly. If a subject is determined to

have delirium, frequency of delirium assessments will increase to daily, Monday through Friday, as scheduling permits, until delirium resolves. The DRS assessments will not be performed if a patient becomes unevaluable due to an acute medical concern (e.g. intubation, sedation, etc.). The CRA(s) or investigators will continue to assess for any toxicity from therapy.

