8.1.4 Serious AE or SAR

An AE or SAR is considered serious if, in the view of either the investigator or sponsor, it results in any of the following outcomes:

- Death;
- Is life-threatening (places the subject at immediate risk of death from the event as it occurred);
- Requires inpatient hospitalization (>24 hours) or prolongation of existing hospitalization;*
- Results in congenital anomaly/birth defect;
- Results in a persistent or significant incapacity or substantial disruption of the ability to conduct normal life functions;
- Important medical events that may not result in death, be life-threatening, or require hospitalization may be considered a serious adverse drug experience when, based upon appropriate medical judgment, they may jeopardize the patient or subject and may require medical or surgical intervention to prevent one of the outcomes listed in the definition. For reporting purposes, also consider the occurrences of pregnancy as an event which must be reported as an important medical event.

*Hospitalization for anticipated or protocol specified procedures such as administration of chemotherapy, central line insertion, metastasis interventional therapy, resection of primary tumor, or elective surgery, will not be considered serious adverse events.

Pregnancy that occurs during the study must also be reported as an SAE.

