8.3 SAEs or Serious SARs

8.3.1 Timing

After informed consent but prior to initiation of study medications, only SAEs caused by a protocol-mandated intervention will be collected (e.g. SAEs related to invasive procedures such as biopsies, medication washout).

For any other experience or condition that meets the definition of an SAE or a serious SAR, recording of the event must begin from day 1 of study treatment and continue through the 30 day follow-up period after treatment is discontinued.

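### The delirium exclusion in 8.1.1 outlasts DRS capture: first-onset delirium after discharge has no required endpoint or AE record, and its SAE status is ambiguous

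*Combined protocol and SAP*

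**What the plan says.** Section 8.1.1 defines an adverse event broadly and then carves out the trial's own outcome: "Development or worsening of delirium should not be recorded as an AE, unless it is attributable by the investigator to the study therapy". It gives no date on which the carve-out ends.

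The primary endpoint (3.1) is a DRS score above 12, with ratings made "three times weekly from day after transplant to 30 days after transplant or discharge, whichever comes first". After discharge, 7.5 provides that at each follow-up visit "delirium assessments (DRS) will also be performed in participants who became delirious during the inpatient phase"; footnote d to the table in 7.1 agrees. Everyone else has the MOCA and the questionnaires at one, three and six months, but no DRS.

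The safety window is longer. Treatment under 5.2 is "thiamine 200 mg IV tid for seven days beginning on the day after of transplant". For serious events, 8.3.1 says "recording of the event must begin from day 1 of study treatment and continue through the 30 day follow-up period after treatment is discontinued", and 8.2 sets the same end point for non-serious events. The schedule in 7.1, however, marks the Adverse Events Form only for post-transplant day 1 and days 2 to 30.

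On seriousness, 8.1.4 begins "An AE or SAR is considered serious if" and lists among its criteria "Requires inpatient hospitalization (>24 hours) or prolongation of existing hospitalization".

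**The concern.** Leaving the study outcome out of the AE data is normal practice when the endpoint captures it. Here the endpoint stops before the exclusion does. Take a hypothetical patient discharged without delirium on day 20 and readmitted on day 26 with a first episode. Under 7.11, discharge ends the required delirium assessment, so the patient is evaluable (given adequate dosing) and counts as a non-event. The episode falls inside the safety window, but 8.1.1 keeps it out of the AE data, and 7.5 schedules no DRS at one month.

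The only exception is attribution to study therapy, judged case by case by investigators who are blinded (7.3). Section 8.1.2 itself names an aggregate comparison of events between groups as one ground for suspecting the drug, and events that are not recorded cannot be aggregated. At stake is the completeness of the safety data, including what the DSMC sees under 8.5. The primary comparison is not at stake.

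**Working it through.** **The plan's own figure.** Section 9.2 gives 80% power for 0.445 versus 0.155 with 30 per arm at one-sided 0.05. With a pooled proportion of 0.30:

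- z = [0.29 × √30 − 1.645 × √(2 × 0.30 × 0.70)] / √(0.445 × 0.555 + 0.155 × 0.845) = (1.588 − 1.066) / 0.615 = 0.85, so power is 80.2%.
- The odds ratio is (0.155/0.845) / (0.445/0.555) = 0.229, as stated.

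The figure reproduces, and nothing in this point changes it.

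**The windows.** Inputs are dosing on days 1 to 7 (5.2), safety recording to 30 days after treatment ends (8.2, 8.3.1), and DRS to day 30 or discharge (3.1). The documents give no discharge day, so the days below are assumptions.

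- End of safety window = last dose day + 30. A full course gives 7 + 30 = day 37. Dosing stopped after day 1 gives 1 + 30 = day 31.
- End of DRS window = the smaller of 30 and the discharge day.
- Gap = end of safety window − end of DRS window.

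| Discharge day (assumed) | Gap, full course | Gap, dosing stopped after day 1 |
|---|---|---|
| 14 | 37 − 14 = 23 days | 31 − 14 = 17 days |
| 21 | 37 − 21 = 16 days | 31 − 21 = 10 days |
| 25 | 37 − 25 = 12 days | 31 − 25 = 6 days |
| 30 | 37 − 30 = 7 days | 31 − 30 = 1 day |

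The gap is positive in every case.

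**SAE status.** Two readings are open.

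- Since 8.1.4 builds a serious event from an AE or SAR, an episode that may not be recorded as an AE cannot become an SAE.
- Alternatively, 8.1.1 restricts only what is recorded as an AE. An episode that required readmission still fulfils the seriousness criteria, and 8.3.1 and 8.5 extend recording to every experience or condition fulfilling the SAE definition.

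No sentence chooses between them, so staff could handle the same event differently from one patient to the next.

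**The case against.** The strongest reply is that the endpoint is doing what it was designed to do. The primary objective (2.1.1) concerns delirium during the transplant hospitalization, so days after discharge are outside it by intention and are not lost endpoint days. That stands.

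It is also fair to say that such a patient is not invisible. An infection or graft-versus-host disease behind the readmission is not excluded and stays reportable. CNS-active drugs are tracked (7.6, with the form running to day 30 in 7.1). All patients have a MOCA at one month. Those already delirious as inpatients have a DRS at one month, give or take two weeks, which can fall inside the safety window. A reader might infer that delirium after discharge is recorded nowhere, or that 8.1.1 forbids every AE or SAE entry for it. The documents support neither: these other traces exist, the attribution exception is explicit, and the SAE bar is only an inference. None of these traces, however, is a required record of a first delirium episode after discharge.

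A reader might also infer that the trial cannot detect delirium that is delayed rather than prevented. Within the admission it can. DRS runs up to day 30, which is 30 − 7 = 23 days after the last dose, and 9.3 compares time to delirium by Kaplan-Meier.

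Finally, one could extend the point to patients in hospital, because of 7.4: "The DRS assessments will not be performed if a patient becomes unevaluable due to an acute medical concern". That is weaker ground. The acute event is itself recordable, a patient who misses the weekly assessments is non-evaluable and replaced under 7.11, and it is unclear how delirium would be diagnosed under sedation. I do not rest the point on it.

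**Conclusion.** The point holds in a limited form. First-onset delirium after discharge, within 30 days of the last dose and not attributed to study therapy, has no required record as an endpoint or an AE. If it causes readmission, its SAE status is ambiguous. After a full course the unprotected interval is 7 days for discharge on day 30 and 12 to 23 days for discharge on days 25 to 14; those discharge days are assumed.

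The number of events cannot be estimated. It is tempting to set, say, 2 to 4 delirious readmissions against the 0.445 × 30 + 0.155 × 30 = 18 delirium events the plan expects, and to report 11% to 22%. The documents contain no readmission rate, so that percentage would only restate the guess. Nor does the 14-fold mortality figure in 1.2 measure the stakes here: it concerns delirium in transplant patients generally, not episodes after discharge.

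This is a gap in the wording of safety capture. It is worth closing because the rule, followed as written, can drop serious events from the safety data. The primary endpoint, its analysis and the sample size are unaffected.

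**What to change.** - In 8.1.1, limit the exclusion to delirium captured by a scheduled inpatient DRS, up to discharge or day 30.
- State that clinically diagnosed delirium after discharge, within the existing safety window, is recorded as an AE, and as an SAE if it meets 8.1.4. This also settles the ambiguity with 8.3.1 and 8.5.
- Add to the safety analyses in 9.3 a descriptive tabulation of these events by arm.
- Align the Adverse Events Form schedule in 7.1, now days 1 to 30, with the window in 8.2 and 8.3.1. Rewording 8.1.1 alone would leave the last week of that window without a scheduled form.

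The cost is short edits to these sections, a CRF instruction and a few extra AE or SAE entries. Those entries would rest on clinical diagnosis rather than the DRS, and ascertainment after discharge would be incomplete. They would therefore inform safety review but would not provide a formal between-arm test of delayed delirium.

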8.1.2 Suspected Adverse Reaction (SAR)

A suspected adverse reaction (SAR) is any AE for which there is a *reasonable possibility* that the drug is the cause. *Reasonable possibility* means that there is evidence to suggest a causal relationship between the drug and the AE. A suspected adverse reaction implies a lesser degree of certainty about causality than adverse reaction, which means any adverse event caused by a drug.

Causality assessment to a study drug is a medical judgment made in consideration of the following factors: temporal relationship of the AE to study drug exposure, known mechanism of action or side effect profile of study treatment, other recent or concomitant drug exposures, normal clinical course of the disease under investigation, and any other underlying or concurrent medical conditions. Other factors to consider in considering drug as the cause of the AE:

- Single occurrence of an uncommon event known to be strongly associated with drug exposure (e.g., angioedema, hepatic injury, Stevens-Johnson Syndrome)
- One or more occurrences of an event not commonly associated with drug exposure, but otherwise uncommon in the population (e.g., tendon rupture); often more than once occurrence from one or multiple studies would be needed before the sponsor could determine that there is *reasonable possibility* that the drug caused the event.

- An aggregate analysis of specific events observed in a clinical trial that indicates the events occur more frequently in the drug treatment group than in a concurrent or historical control group

8.1.3 Unexpected AE or SAR

An AE or SAR is considered unexpected if the specificity or severity of it is not consistent with the applicable product information (e.g., package insert/summary of product characteristics for an approved product). Unexpected also refers to AEs or SARs that are mentioned in the IB as occurring with a class of drugs or as anticipated from the pharmacological properties of the drug, but are not specifically mentioned as occurring with the particular drug under investigation.

8.1.4 Serious AE or SAR

An AE or SAR is considered serious if, in the view of either the investigator or sponsor, it results in any of the following outcomes:

- Death;
- Is life-threatening (places the subject at immediate risk of death from the event as it occurred);
- Requires inpatient hospitalization (>24 hours) or prolongation of existing hospitalization;*
- Results in congenital anomaly/birth defect;
- Results in a persistent or significant incapacity or substantial disruption of the ability to conduct normal life functions;
- Important medical events that may not result in death, be life-threatening, or require hospitalization may be considered a serious adverse drug experience when, based upon appropriate medical judgment, they may jeopardize the patient or subject and may require medical or surgical intervention to prevent one of the outcomes listed in the definition. For reporting purposes, also consider the occurrences of pregnancy as an event which must be reported as an important medical event.

*Hospitalization for anticipated or protocol specified procedures such as administration of chemotherapy, central line insertion, metastasis interventional therapy, resection of primary tumor, or elective surgery, will not be considered serious adverse events.

Pregnancy that occurs during the study must also be reported as an SAE.

8.2 Documentation of non-serious AEs or SARs

For non-serious AEs or SARs, documentation must begin from day 1 of study treatment and continue through the 30 day follow-up period after treatment is discontinued.

Collected information should be recorded in the Case Report Forms (CRF) for that patient. Please include a description of the event, its severity or toxicity grade, onset and resolved dates (if applicable), and the relationship to the study drug. Documentation should occur at least monthly.

8.3 SAEs or Serious SARs

8.3.1 Timing

After informed consent but prior to initiation of study medications, only SAEs caused by a protocol-mandated intervention will be collected (e.g. SAEs related to invasive procedures such as biopsies, medication washout).

For any other experience or condition that meets the definition of an SAE or a serious SAR, recording of the event must begin from day 1 of study treatment and continue through the 30 day follow-up period after treatment is discontinued.

8.3.2 Documentation and Notification

SAEs or Serious SARs must be recorded in the SAE console within Oncore™ for that patient within 24 hours of learning of its occurrence. Additionally, the NCCN Project Manager must also be notified via email of all SAEs within 24 hours of learning of its occurrence.

8.4 Adverse Event Reporting

8.4.1 IRB Reporting Requirements:

UNC:

- The UNC-IRB will be notified of all SAEs that qualify as an Unanticipated Problem as per the UNC IRB Policies using the IRB's web-based reporting system (see section 10.5.3) within 7 days of the Investigator becoming aware of the problem.

8.4.2 Funding Source (e.g. Manufacturer) Reporting Requirements:

N/A

8.5 Data and Safety Monitoring Plan

This is a Phase II, single site study of 60 individuals to gather preliminary data on the efficacy and safety of high dose IV thiamine for delirium prevention in patients undergoing HSCT. We will follow our standard protocol for monitoring of clinical trials. Subjects are screened to ensure that there are no contraindications to their participation.

The study Co-PIs, Drs. [name] and [name], will be responsible for continuous monitoring of patient safety during the trial. For non-serious Adverse Events (AEs), documentation will begin from the first day of study treatment and continue through the 30 day follow-up period after treatment is discontinued. Collected information will be recorded in Case Report Forms (CRF) for that patient. A description of the event, its

severity or toxicity grade, onset and resolved dates (if applicable), and the relationship to the study drug will be included. For any experience or condition that meets the definition of a serious adverse event (SAE), recording of the event will begin after signing of the informed consent and continue through the 30 day follow-up period after treatment is discontinued. These events will be recorded in the CRF for that patient within 24 hours of learning of its occurrence. If the event is both serious AND unexpected, it will also be recorded on the MedWatch Form 3500A, as per 21 CFR 312.32, and forwarded to the FDA in accordance with 21 CFR 314.80 (for marketed drugs). The UNC IRB will be notified of all SAEs that qualify as an Unanticipated Problem (serious, unexpected, and related) as per the UNC IRB policies. In accordance with these policies, an aggregated list of all SAEs will be submitted to the UNC IRB annually at the time of study renewal.

Periodic review, at an interval of every six months to annually, by the Lineberger Comprehensive Cancer Center Data Safety Committee (LCC DSMC), Protocol Review Committee (PRC), and Office of Human Research Ethics (OHRE) Biomedical IRB will provide oversight of the Co-PIs' continuous monitoring. For each DSMC review, summary information regarding toxicity and accrual patterns will be prepared and submitted by the Co-PIs. Specific information submitted for review includes: (1) The number of patients enrolled, consented, consented but not treated, currently being treated, completed treatment, the number of patients who did not complete treatment and the reasons for coming off study; (2) Grade 3 or greater reported Adverse Events to date; (3) Serious Adverse Events and Unanticipated Problems since last report, with assurance of reporting to internal and external regulating bodies; (4) Exceptions in eligibility or treatment and significant protocol deviations/violations; (5) Significant literature reporting developments that may affect the safety of participants or the ethics of the study; (6) Summaries of team meetings that have occurred since the last report; (7) Results of interim analyses required by the protocol. We will also be submitting a preliminary report of response and other endpoints listed in the primary and secondary objectives of the protocol for DSMC review.

Though no formal *a priori* stopping rules are proposed for the study, in the event of a serious or unexpected adverse event or frequent occurrence of less serious unexpected or expected adverse events we will consult with the OHRE and DSMC as to whether the trial should continue.

